8.7. Data Analysis

Detailed methodology for summary and statistical analyses of data collected in this study will be documented in an SAP for the feasibility assessment and the respective SCRI and cohort safety analyses. All analyses will be conducted using R version R-4.0.3 or higher (Foundation for Statistical Computing, Vienna, Austria; <https://www.R-project.org>) or SAS version 9.3 software or higher (Cary, North Carolina, USA; SAS Institute, Inc.). The SAP will contain more detail about the analysis and data pooling and may modify the plans outlined in the protocol; any major modifications of primary endpoint definitions or their analyses would be reflected in a protocol amendment.

A general description of the planned statistical methods to be used to analyse the data collected in this study is presented in the following subsections. Additional details will be provided in the SAP. A summary of planned analyses is provided in [Table 5](#).

Table 5: Summary of Planned Analyses

Analysis	Acute AESIs Study design	Non-acute Study design for Non-acute AESIs	Risk window Definition of Risk window	Notes on the main purpose of analysis/difference from the primary analysis
Feasibility	Cohort	Cohort	none	Baseline characteristics, vaccine uptake, assessing the quality of data and of algorithms for outcomes and covariates, and the number of outcomes and time-to-event.
Primary (Final)	SCRI: post-vaccination control window	Cohort: exposed versus concurrent unexposed comparator and versus other COVID-19 vaccine exposed	Disease-specific risk window	SCRI: Using a pre and post-vaccination control window to assess the effect of the order of windows; Calculating and comparing the incidence rates of each AESI; Analysis of negative control data
Secondary (Final)	Subpopulation SCRI	Subpopulation cohort	Disease-specific risk window	Sub-population analysis
Sensitivity (Final)	Cohort: exposed versus concurrent unvaccinated comparator and/or versus other COVID-19–vaccine exposed	Cohort: exposed versus concurrent unexposed comparator and versus other COVID-19 vaccine exposed	Extended risk windows for acute events	Acute events: Compare different analytical approaches and incorporate the use of extended risk windows; Non-acute: not applicable
Sensitivity (Final)	SCRI: Comparing Ad26.COV2.S with active comparators with (1) only 1 dose and (2) a 2-dose strategy	Cohort: Comparing Ad26.COV2.S with active comparators with (1) only 1 dose and (2) a 2-dose strategy	Disease-specific risk window	Address the different dosing schedules between Ad26.COV2.S and the comparator vaccines used in the analyses
Sensitivity (Final)	SCRI, pre-vaccination control window	Cohort analyses with non-exposed restricted to data sources with good ascertainment of COVID-19 vaccine exposure	Disease-specific risk window	SCRI: Using a pre- and post-vaccination control window to assess the effect of the order of windows; Cohort: Restricted analysis to avoid misclassification of unvaccinated status; Risk window
Sensitivity (Final)	SCRI, excluding and censoring upon taking other (non-COVID-19) vaccinations	Cohort, excluding and censoring upon taking other (non-COVID-19) vaccinations	Disease-specific risk window	To avoid the confounding effects of non-COVID-19 vaccines
Stratified analysis (Final)	SCRI: pre-vaccination and post-vaccination control window	Cohort: exposed versus concurrent unexposed comparator and versus other COVID-19 vaccine exposed	Disease-specific risk window	Subgroup analysis according to the baseline factors such age and sex

AESI= adverse event of special interest; SCRI= self-controlled risk interval

Note: Acute AESIs are events expected to occur within 60 days of vaccination; non-acute events are events expected to be recorded >60 days after vaccination.

8.7.1. Main Summary Measures

For the feasibility analysis the utilisation patterns of Ad26.COV2.S and other COVID-19 vaccines will be characterised and monitored over time. Description of demographics and clinical characteristics will be reported overall and for different groups of vaccine recipients.

The primary analysis will focus on calculating and comparing the incidence rates of each non-acute AESI between individuals exposed to Ad26.COV2.S and (1) unexposed individuals; (2) individuals exposed to another viral vector COVID-19 vaccine (i.e., Vaxzevria® [AZD1222] by Oxford/AstraZeneca); and 3) individuals exposed receiving a mRNA COVID-19 vaccine (cohort).

For acute events, the relative risk between risk window and control window will be estimated (using an SCRI design) among individuals exposed to Ad26.COV2.S. All analyses will be conducted within each data source and pooled across data sources using a random-effects model.

For the COVID-19 vaccines with a 2-dose schedule, AESI-specific risk windows after each dose of the comparator will be considered for the analyses. Further details on how to deal with different doses will be included in the SAP.

8.7.1.1. Feasibility Analysis

Demographic and Baseline Characteristics

The distributions of baseline characteristics at start of COVID-19 vaccination for each COVID-19 vaccine exposure group will be calculated to describe differences between the groups. For continuous variables, means, standard deviations, medians, and other quartiles will be estimated. For categorical variables, counts and proportions will be estimated. The missingness of variables will also be described.

Vaccine uptake

For every data source, the number of administered doses per COVID-19 vaccine brand within the primary series (dose 1 and dose 2) will be calculated by calendar time (in months) over the follow-up period.

For individuals with a given year of birth vaccination uptake for dose 1 over time will be calculated. The coverage at month i for birth year j is calculated by dividing the number of vaccinated individuals n_{ij} by the total number of individuals under follow-up at month i (N_{ij}), expressed as a percentage. Estimates of vaccination uptake will be compared with data provided by ECDC.

Algorithms for outcome definitions

For each outcome, the number of cases by diagnosis code will be counted, and the impact on the case count will be assessed when confirmatory medications /procedures or laboratory tests are used. All such counts will be stratified by meaning (GP record, hospitalisation primary diagnosis, hospitalisation secondary diagnosis).

Time-to-onset

Descriptive analyses of the time-to-onset of event (up to one year after vaccination) may inform the selection of risk intervals for the sensitivity analyses.

8.7.1.2. Cohort Design**Demographic and Baseline Characteristics**

The distributions of baseline characteristics at index date by exposure group will be calculated to describe the study cohort and illustrate differences between the groups. For continuous variables, means, standard deviations, medians, and other quartiles will be estimated. For categorical variables, counts and proportions will be estimated. The missingness of variables will also be described. Comparative analyses will be included in the final report. Further details will be described in the SAP. To describe the relative imbalance of characteristics between exposed and unexposed groups, absolute standardised differences will be calculated for each baseline characteristic. Multilevel categorical variables will calculate an overall standardised difference across all levels. The larger the absolute standardised difference values, the greater the imbalance between baseline characteristics.

Measures of Occurrence and Association

Incidence rates for each AESI will be calculated by dividing the number of cases by the follow-up person-time. Poisson regression models will estimate incidence rate ratios and 95% CIs. Robust variance estimation will account for an individual's possibility to be included in the exposed and unexposed cohorts. The Poisson model for each AESI will include the number of events in each cohort as the dependent variable, the exposure status as the binary independent variable, and the natural logarithm of the person-time as the offset variable. The attributable risk will be computed as the difference between the incidence rate in the exposed cohort and the incidence rate in the unexposed cohort.

Adjustment for Baseline Imbalances

Individuals following in the exposed and non-exposed groups may have different characteristics that may determine their risk of AESI. To account for such potential confounding, key variables will be matched, and it will be explored whether other covariates are associated with exposure and also whether they are independent risk factors for the outcome (Poisson regression) in the non-exposed. If many factors are imbalanced between the matched cohorts, a propensity score will be created; if only a few are imbalanced, there will be an adjustment for all factors that are both associated with exposure and outcome. Also, if the number of events is low, the use of propensity score methods for adjustment will be considered. More details will be provided in the SAP.

8.7.1.3. Self-controlled Risk Interval Design**Descriptive Statistics**

The number of cases of each AESI will be reported in the control and risk windows, overall and by important covariates.

Measures of Association

Conditional Poisson regression will be used to estimate incidence rate ratios and 95% confidence intervals (CIs). The SCRI inherently adjusts for both measured and unmeasured time-constant factors such as sex and chronic health conditions with onset before the start of follow-up. Time-varying confounders (e.g., medications and other vaccinations) may be included as covariates in regression models. Subgroup analyses will be conducted by groups defined by demographic and clinical characteristics and other covariates of interest.

8.7.2. Main Statistical Methods

8.7.2.1. Matching

For the cohort designs, matching will be used to ensure comparability on observed covariates between groups to be compared. There will be a match on the following key variables at index date:

- Age (year of birth)
- Sex
- Pregnancy status
- Immunocompromised state
- Prior COVID-19 infection
- Calendar time (with calliper approach) Prior recorded COVID-19 infection (yes/no)
- Presence of one or more risk factors for severe COVID-19 (e.g., cancer, sickle cell disease, obesity, chronic kidney disease, chronic respiratory disease, human immunodeficiency virus infection).

For the SCRI design, an individual is matched with itself, and therefore analyses will be controlled for all stable variables.

8.7.3. Secondary Analyses

Analyses within the primary study designs (cohort design for non-acute events and SCRI design for acute events) will be conducted for sub-populations:

- Immunocompromised individuals,
- Pregnant women,
- Individuals who have a prior history of thrombotic events and/or thrombocytopenia,
- Prior COVID-19 infection (yes/no),
- Individuals with a prior history (ever) of the specific event more than a year before start of follow-up.

8.7.4. Stratified Analyses

Analyses within the primary study designs (cohort design for non-acute events and SCRI design for acute events) will be stratified by the clinically relevant subgroups below. Stratification will be done also for matching variables when considered relevant.

- Selected comorbidities, including risk factors for severe COVID-19 (by presence or absence of each comorbidity)
- Frailty score (categorised)
- Age (0-17, 18-29, 30-39, 40-49, 50-59, 60-69, 70-79, 80+ years)
- Sex.

8.7.5. Missing Values

Further details of the analysis, including handling of missing data, will be described in the SAP.

8.7.6. Sensitivity Analyses

Sensitivity analyses will be performed to:

- Assess the risk of AESI within extended disease-specific risk windows for events for which the risk interval is not well known or documented in the vaccine safety literature.
- Assess the impact of data sources that are shown not to capture vaccinations well during the feasibility assessment. In the sensitivity analyses with non-exposed comparators those data sources from the cohort analysis for the acute and non-acute events will be excluded, to avoid misclassification of exposure.
- Excluding and censoring upon the administration of other (non-COVID-19) vaccinations in the SCRI and cohort study (see Section 8.1.2.2).
- Comparing Ad26.COV2.S with active comparators with (1) a 1-dose strategy and (2) a 2-dose strategy in the cohort study.
- Conduct a SCRI analysis using a pre-vaccination control window for all acute AESIs.

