On 27 February 2021, the US Food and Drug Administration (FDA) granted an emergency use authorisation (EUA) for the Ad26.COV2.S vaccine for use in individuals 18 years of age and older ([FDA 2021](#)). On 11 March 2021, European Medicines Agency (EMA) granted a conditional marketing authorisation (cMA) for Ad26.COV2.S for use in individuals 18 years of age and older ([EMA 2021](#)). The UK Medicines and Healthcare products Regulatory Agency (MHRA) granted a cMA on 28 May 2021 ([MHRA 2021](#)).

As of 12 April 2021, more than 6.8 million doses of the Ad26.COV2.S vaccine have been administered in the US. Up to that date, 6 cases of cerebral venous sinus thrombosis (CVST) along with low platelet counts were reported ([Cines 2021](#)). In response to these cases, the US FDA and the Centers for Disease Control and Prevention (CDC) recommended a pause in the use of the Ad26.COV2.S vaccine in the US on 13 April 2021, to allow for further investigations on these rare events of thrombosis with thrombocytopenia. Similar cases of thrombosis with thrombocytopenia had also been reported in individuals who received the Vaxzervria/COVID-19 AstraZeneca Vaccine outside the US ([Greinacher 2021](#), [Schultz 2021](#), [Scully 2021](#)). This syndrome has been termed “vaccine-induced prothrombotic immune thrombocytopenia (VIPIT)” or “vaccine-induced immune thrombotic thrombocytopenia (VITT)” but is now named “thrombosis with thrombocytopenia syndrome (TTS)”. This rare and new syndrome is characterised by thrombosis (such as CVST or splanchnic thrombosis), thrombocytopenia and confirmed with a positive platelet factor 4 (PF4)-heparin enzyme-linked immunosorbent assay. There is currently no standard case definition for TTS accepted for use by all countries. In this regard, the Brighton Collaboration developed an interim case definition of TTS ([Brighton Collaboration 2021](#)). VAC4EU organised a webinar to discuss the operationalisation of this event, for which background rates were generated for EMA ([Willame 2021](#)). In addition, the PRAC’s recommendation for the categorisation of TTS will be taken into account.

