- Following the AESI notification to EMA a Type 2 variation was submitted on 25 June 2021 to update the European Union Product Information (EUPI) with a contraindication for individuals who have previously experienced episodes of CLS. In addition, an updated direct healthcare professional communication to inform healthcare professionals of the contraindication for individuals who have previously experienced episodes of CLS was submitted to EMA on 25 June 2021. Upon EMA request wording related to CLS was also added to sections 4.4 and 4.8 of the EUPI. This variation was approved on 09 July 2021.
- In the US Janssen notified the FDA of the internally identified significant safety issue around cases of CLS reported with Ad26.CoV2.S. also on 18 June 2021 and submitted as per guidance obtained from the FDA a Clinical Overview which included an executive summary for CLS and a cumulative review that includes supportive data, narratives and Council for International Organizations of Medical Sciences on 25 June 2021.

On 7 July 2021, based on an FDA review of cases of Guillain-Barré syndrome (GBS) reported in recipients of the Janssen COVID-19 Vaccine, FDA required updates to the product label to include a warning statement and associated information regarding GBS following vaccination. Janssen agreed to consider GBS a significant safety issue. In addition, FDA provided comments regarding their review of capillary leak syndrome (CLS). FDA did not conclude that in individuals with a history of CLS, the risk of receiving the Janssen COVID-19 vaccine clearly outweighs any possible

benefit and the agency believes it is appropriate to include CLS in Section 6.2 Post Authorisation Experience of the Fact Sheet for Healthcare Providers Administering Vaccine (Vaccination Providers). On 8 July 2021, Janssen submitted updated factsheets to the EUA accepting the FDA positions on GBS and CLS. Approval was received on 12 July 2021.

On 12 July 2021, a type II variation was submitted to EMA to update the EUPI to include GBS as an Adverse Drug Reaction (ADR) in section 4.8 and to include related wording in Section 4.4 of the EUPI.

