 - thrombotic events (microangiopathy including capillary leak syndrome), disseminated intravascular coagulation, deep vein thrombosis, pulmonary embolism, cerebral vein thrombosis, peripheral thrombosis, thrombosis with thrombocytopenia and ischemic strokes, acute coronary syndrome (acute myocardial infarction, unstable angina, and new onset angina),
 - bleeding events including haemorrhagic stroke (no subarachnoid),
 - composite endpoint: Venous thrombosis (including pulmonary embolism and deep vein thrombosis)
 - composite endpoint: Arterial thrombosis (including acute coronary syndrome and ischemic stroke),
 - composite endpoint: stroke (including haemorrhagic and non-hemorrhagic stroke)
 - heart failure, and stress cardiomyopathy.
- The incidence of immune/inflammatory events: encephalitis (including acute demyelinating encephalomyelopathy and meningoencephalitis), Guillain-Barré Syndrome, Bell's palsy, immune thrombocytopenia, thrombocytopenia, transverse myelitis and cardiac inflammatory disorders (including myocarditis and pericarditis) within 1-42 days.
- The incidence of sensorineural hearing loss within 1-60 days.
- The incidence of asthma exacerbation within 1-14 days.

Non-acute events (events expected to be recorded >60 days after vaccination)

- The incidence of new-onset autoimmune thyroiditis, multiple sclerosis, acute aseptic arthritis, and type 1 diabetes mellitus within 1-365 days.

Newly identified AESI may be incorporated into the list of AESI to be investigated by the current study if a safety signal occurs.

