8.1.2.1. Self-controlled Risk Interval Design (Primary Study Design for Acute Events)

The SCRI design will compare the risk of the AESI in a post-vaccination risk window to a pre-vaccination control window (sensitivity analysis) and post-vaccination control window (main analysis) within the same individual.

The SCRI design will include only individuals in the primary analysis who received at least one first-ever dose of the Ad26.COV2.S vaccine during the study period. Vaccinated individuals enter the study at the date of the start of the pre-vaccination control window. The SCRI design will compare the risk of each outcome during the post-vaccination risk window following the COVID-19 dose with a self-matched control interval that may be prior to vaccination, or after the vaccination risk window, to assess the baseline risk of the outcome. The control window will have the same maximum length as the risk window to minimise time-varying confounding that cannot be measured. In case the follow-up time does not capture the maximum post-vaccination risk or control window due to right censoring, all available follow-up time will be utilized. Follow-up will be censored upon vaccination with another COVID-19 vaccine or end of follow-up. A washout period between the control and risk window will be applied to minimise capturing of prevalent events during the risk window. A post-vaccination control window may induce a bias towards the null when an AESI that was identified during the vaccination risk window, is captured again during the control window due to a re-admission instead of reoccurrence of the AESI. This situation is more likely to be encountered for acute potentially recurring events such as cardiac events (including acute coronary syndrome, myocarditis, pericarditis, arrhythmia, and stress cardiomyopathy). Moreover, due to lag-times in updating the relevant databanks, there is a higher risk that the post-vaccination control window may not capture all events and underestimate the rate of events. Use of a pre-vaccination control window will deal with these issues. In a sensitivity analyses, we will use a pre-vaccination control window and a post-vaccination control window will be used for the main analysis. In a sensitivity analysis, vaccination to other non-COVID-19 vaccines will also be an exclusion and censoring event.

We will also compare the Ad26.COV2.S vaccine with active comparators with 1) only 1-dose strategy and 2) a 2-dose strategy.

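### The pre-vaccination-window SCRI is required for microangiopathy including capillary leak syndrome (CLS) although previous CLS became a labelled contraindication, so that one sensitivity ratio is biased upward in expectation

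*Protocol*

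**What the plan says.** - **Scope of the analysis.** Protocol section 8.7.6 lists, among the sensitivity analyses, "Conduct a SCRI analysis using a pre-vaccination control window for all acute AESIs". The abstract repeats this, and Table 5 lists the pre-vaccination window as a sensitivity analysis and again under the stratified analyses. None of these places makes an exception.
- **CLS is part of an acute endpoint.** Section 7 lists, for days 1 to 28, "thrombotic events (microangiopathy including capillary leak syndrome), disseminated intravascular coagulation" and other events. Table 1 has a single row, Microangiopathy, with the same window. It has no separate row for CLS.
- **Exposure rule.** Section 6.1 reports a submission on 25 June 2021 to "update the European Union Product Information (EUPI) with a contraindication for individuals who have previously experienced episodes of CLS", and then: "This variation was approved on 09 July 2021". The same section dates the conditional EU authorisation to 11 March 2021.
- **Who enters the SCRI.** Section 8.2.4.2 admits only people who received Ad26.COV2.S in the study period and had the event in the control or risk window.
- **Role of the two windows.** Section 8.1.2.1 makes the post-vaccination control window the main analysis and the pre-vaccination window a sensitivity analysis. It names two weaknesses of the post-vaccination window, re-admissions counted as new events and data lag, and adds: "Use of a pre-vaccination control window will deal with these issues". Table 5 gives the purpose of using both windows as checking whether their order matters.

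**The concern.** A pre-vaccination control window gives a fair baseline only if an event in it does not alter the chance of being vaccinated later. For CLS the protocol itself reports a rule that does alter it. Once the contraindication applies, a person with CLS in the control window should not be vaccinated, and so never becomes an SCRI case. A person with CLS in the risk window has already been vaccinated and is counted. The loss is one-sided.

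The buffer in section 8.1.3 does not help. It is meant for residual risk and prevalent events, and a contraindication based on any previous episode does not lapse after a fixed number of days. No section deals with an event that prevents later vaccination. The closest remark, in the amendment table, is that a post-vaccination window helps with the healthy vaccinee effect.

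At stake is the comparison of the two windows for an endpoint that contains a safety issue the sponsor itself notified to the regulator. A higher pre-window ratio could be read as an effect of window order, or as support for a vaccine risk, when part of it reflects who may be vaccinated.

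**Working it through.** **1. The plan's own figures.** The protocol gives no figure for this bias. Its SCRI power figures show the equal-window set-up it assumes. With p = RR/(1+RR), A = 2[p ln RR − ln((RR+1)/2)], B = p(1−p)(ln RR)²/A and power = Φ((√(nA) − 1.96)/√B), taking two-sided alpha 0.05 (not stated in the protocol):

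- RR = 2 gives p = 0.667, A = 0.1133, B = 0.943.
- n = 100: (3.366 − 1.96)/0.971 = 1.448, power 92.6%, as in Table 3.
- n = 69: (2.796 − 1.96)/0.971 = 0.861, power 80.5%, as in Table 4.

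These tables reproduce; nothing in them is in dispute.

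**2. The bias.** Let λ be the expected number of control-window events before any loss, and θ the true ratio. With equal windows (section 8.1.2.1):

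- risk-window events: θλ
- control-window events kept: λ(1 − q)
- expected ratio, approximately: θλ / [λ(1 − q)] = θ/(1 − q)

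The ratio can only move up. The loss is q = c × f × h, where c is the CLS share of the microangiopathy endpoint, f is the share of vaccinations given after the contraindication, and h is adherence to it. What matters for f is the vaccination date, not the event date. The documents give none of the three, so all values below are assumptions. The calculation takes the washout to precede the control window, as the abstract states; Table 1 words it relative to the index date.

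| c | f | h | q | Ratio when θ = 1 |
|---|---|---|---|---|
| 0.10 | 0.25 | 0.5 | 0.0125 | 1.01 |
| 0.10 | 1 | 1 | 0.10 | 1.11 |
| 0.25 | 0.5 | 0.8 | 0.10 | 1.11 |
| 0.50 | 0.5 | 0.5 | 0.125 | 1.14 |
| 0.50 | 0.5 | 1 | 0.25 | 1.33 |
| 0.50 | 1 | 1 | 0.50 | 2.00 |

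If CLS is 10% of the endpoint, the factor cannot exceed 1/(1 − 0.10) = 1.11.

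**3. How many events might be involved.** Section 8.5 assumes up to 10% of 18.1 million vaccinated, that is 1.81 million. Over 28 days this is 1.81 million × 28/365.25 ≈ 139,000 person-years. The protocol gives no rate for this endpoint. Borrowing two rows of Table 2 as assumed rates:

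- 1 per 100,000 person-years: about 1.4 control-window events
- 10 per 100,000 person-years: about 14
- 1 per 100,000 at the minimum target of 100,000 exposed: under 0.1

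**4. False signals if events were plentiful.** Start from 69 events in total under no effect, 34.5 per window. After loss, n = 34.5 + 34.5(1 − q). The chance of a significant increase, by the normal approximation to the binomial, is about 6% at q = 0.10 (n = 66) and 19% at q = 0.25 (n = 60), against a nominal 2.5%. Reaching 34.5 events per window needs 34.5/139,000 ≈ 25 per 100,000 person-years at the maximum assumed uptake, so these are upper-end illustrations.

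**The case against.** The strongest reply is that the effect is small and confined. CLS is one component of one endpoint in one sensitivity analysis, vaccinations from the March 2021 authorisation up to July 2021 fall outside the contraindication, and events are probably so few that imprecision would outweigh the bias. All of that stands. It limits the size but does not change the direction.

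It is also fair that the main SCRI already uses the post-vaccination window and that a matched cohort is already planned as a further check on acute events. Any divergence would therefore be visible beside the primary result. But visibility does not tell the reader how to interpret the divergence, and Table 5 points to an explanation, window order, that need not be the right one here.

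A reader might infer that the ratio would be doubled, multiplied by five, or left with no control events at all. Those results need q of 0.5, 0.8 and 1, and the last two in effect need an analysis of CLS alone or nearly so. Table 1 lists no such endpoint. A reader might also infer that the sentence in section 8.1.2.1 in favour of the pre-vaccination window is wrong. It is not: it refers to re-admission and data lag, and the pre-vaccination window avoids both.

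Finally, other serious events may also delay vaccination, so CLS is not the only possible case of event-dependent exposure. It is the one for which the protocol itself reports a formal exposure rule, which is why a specific exception is warranted.

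**Conclusion.** The point holds in a limited form. Applying the pre-vaccination-window SCRI without exception to microangiopathy including CLS produces a sensitivity ratio biased upward in expectation by 1/(1 − q) for that endpoint. The direction follows from three statements in the protocol: the unqualified scope, the contraindication, and entry restricted to vaccinees. The size is unknown because the CLS share, the share vaccinated after July 2021 and the adherence are not given; assumed q of 0.10 and 0.25 give 1.11 and 1.33.

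The documents do not support saying that the analysis will show an excess. The observed estimate may be dominated by chance, and the bias may be close to nil if CLS is a small part of the endpoint or most vaccinations were early. Nor do they support saying that the primary result is distorted: the post-vaccination-window estimate does not lose control events in this way. This is a low-severity correction to the scope and interpretation of one sensitivity analysis.

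**What to change.** In section 8.7.6, in the matching line of the abstract and wherever Table 5 names the pre-vaccination window, add an exception for microangiopathy including CLS. Either restrict the pre-vaccination-window SCRI for this endpoint to vaccinations given before the 2021 contraindication, or omit it. Add one sentence stating that a difference between the pre- and post-vaccination results for this endpoint is not to be read as an effect of window order or of the vaccine.

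The post-vaccination-window SCRI and the matched cohort stay as planned, and section 8.1.2.1 needs no change. The edit takes a few lines. Its price is a smaller or missing sensitivity estimate for one AESI; a restricted estimate will rest on fewer events.
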